8.1 MLN9708 (Ixazomib citrate)

8.1.1 Other Names

Ixazomib ML0070120, MLN2238 citrate ester, Ninlaro®

8.1.2 Classification

Proteasome inhibitor

8.1.3 Mode of Action

Ixazomib/placebo is a reversible proteasome inhibitor. Ixazomib/placebo preferentially binds and inhibits the chymotrypsin-like activity of the beta 5 subunit of the 20S proteasome. It induced apoptosis of multiple myeloma cell lines in vitro.

8.1.4 Storage and Stability

Storage: Store ixazomib/placebo capsules between 2° – 30°C (36° – 86°F). Ixazomib/placebo should remain in the blister and carton provided until use. Do not freeze or store above 30°C.

If a storage temperature excursion is identified, promptly return ixazomib/placebo capsules to 2° – 30°C (36° – 86°F) and quarantine the supplies. Provide a detailed report of the excursion (including documentation of temperature monitoring and duration of the excursion) to [contact] for determination of suitability.

Stability: Stability studies are ongoing.

8.1.5 Dose Specifics
Ixazomib/placebo will be administered at a dose of 4 mg on days 1, 8, and 15 of each cycle.

8.1.6 Preparation
No specific preparation is required.

NOTE: Ixazomib/placebo is an anticancer drug. As with other potentially toxic compounds, caution should be exercised when handling ixazomib/placebo. It is recommended to wear gloves and protective garments during preparation when dispensed in clinic. Please refer to published guidelines regarding the proper handling and disposal of anticancer agents.

8.1.7 Route of Administration
Ixazomib/placebo will be administered orally.

8.1.8 Method of Administration
Take capsule(s) on an empty stomach, 1 hour before or 2 hours after food. Swallow whole capsules with water. Do not open or break capsules.
Missed or delayed dose can be taken only if the next scheduled dose is \geq 72 hours away. A missed dose should not be taken within 72 hours of the next scheduled dose. If vomiting occurs after taking a dose, the patient should not repeat the dose. Resume dosing at the time of the next scheduled dose.

8.1.9 Availability
Clinical Supplies: Ixazomib (NSC 767907) and matching placebo will be provided free of charge by Takeda and distributed by the Pharmaceutical Management Branch (PMB), Cancer Therapy Evaluation Program (CTEP), Division of Cancer Treatment and Diagnosis (DCTD), National Cancer Institute (NCI).
Ixazomib and matching placebo will be supplied in blister cards containing 3 capsules each.
Each blinded, patient-specific blister card will be labeled with:

- the protocol number (i.e., "EAA171")
- the blister card number (i.e., "blister card 1 of 2" or "blister card 2 of 2")
- the number of capsules (i.e., "3 capsules")
- the patient ID number (e.g., "99999", which represents the unique patient identifier assigned at registration)
- the patient initials (i.e., first initial, middle, last initial [e.g., "FML"])
- the agent identification (i.e., "Ixazomib 4 mg or placebo capsule", "Ixazomib 3 mg or placebo capsule" or "Ixazomib 2.3 mg or placebo capsule")

- a blank line for the pharmacist to enter the patient's name
- administration instructions (i.e., "Take one capsule on days 1, 8 and 15 of each 28-day cycle.")
- storage instructions [i.e., "Store between 2° – 30° C (36° – 86° F)."]
- emergency contact instructions
- a Julian date

The Julian date indicates the day the bottle was labeled and shipped and is composed of the last two digits of the calendar year (e.g., 2019 = 19, 2020 = 20) and a day count (e.g., January 1 = 001, December 31 = 365). For example, a bottle labeled and shipped on January 1, 2019 would have a Julian date of '19001' and a bottle labeled and shipped on December 31, 2019 would have a Julian date of '19365'. The Julian date will be used by PMB for recalls. When a lot expires, PMB will determine the last date the expired lot was shipped and will recall all bottles (i.e., both Ixazomib and Placebo) shipped on or before that date thus eliminating any chance of breaking the blind. **The Julian Date – Order number (e.g., 21352-0003) from the patient-specific label must be used as the Lot number on the NCI Oral DARF.**

BLINDED AGENT ORDERS: No blinded starter supplies will be available for this study.

Patients will be registered and randomized through OPEN and assigned patient ID number. This number must be recorded by the registering institution at the time of registration for proper clinical supply dispersion. Once a patient has been registered, ECOG-ACRIN will electronically transmit a clinical drug request for that patient to the PMB. This request will be entered and transmitted by ECOG-ACRIN the day the patient is registered and will be processed by PMB the next business day and shipped the following business day. If a patient is registered on Monday, ECOG-ACRIN would enter a clinical drug request for that patient on Monday and PMB would process that request on Tuesday and ship the drug on Wednesday. Sites could expect to receive their order approximately Thursday or Friday. Shipments to United States sites can be expedited (i.e., receipt on Thursday in example above) by the provision of an express courier account name and number to ECOG-ACRIN at the time the patient is registered/randomized.

The initial patient-specific supply will be enough to complete 8 weeks of treatment (2 x 3-capsule blister cards). The supplies will be sent to the registering investigator / drug shipment investigator at the time of registration and should arrive within 5 to 7 business days. Subsequent orders for blinded, patient-specific supplies must be requested by the Principal Investigator (or his/her authorized designee[s]) for EAA171 at each participating institution using the PMB On-line Agent Order Processing (OAOP) program. The assigned patient ID number (e.g., 999999) and the patient initials (e.g., "FML") should be entered in the "Patient or Special Code" field. A separate order is required for each patient ID number (e.g., 999999) being ordered. All drug orders should

be shipped directly to the physician responsible for treating the patient. Requests can be placed **6 weeks after the last shipment is received**.

DOSE ADJUSTMENTS: Starter supplies for dose reductions will not be provided. If the patient is dose reduced from the original 4 mg or placebo dose, an agent request must be submitted by the site through the OAOP application. Ixazomib/placebo 3 mg and 2.3 mg dose adjustments will be ordered through OAOP only at the time of the dose reduction. The patient-specific blister cards of the dose adjusted supplies will be enough to complete 8 weeks of treatment (2 x 3-capsule blister cards). Requests for additional supplies can be placed **6 weeks after the last shipment is received**.

Pharmaceutical Management Branch (PMB) policy requires that agent be shipped directly to the institution where the patient is to be treated. The CTEP-assigned protocol number and patient ID must be used for ordering all CTEP-supplied investigational agents for this study. The responsible investigator must be registered with CTEP, DCTD through an annual submission of FDA Form 1572 (Statement of Investigator), NCI BioSketch, Agent Shipment Form (ASF), and Financial Disclosure Form (FDF).

Active CTEP-registered investigators and investigator-designated shipping designees and ordering designees must submit agent requests through the PMB Online Agent Order Processing (OAOP) application. Access to OAOP requires the establishment of a CTEP Identity and Access Management (IAM) account and the maintenance of an “active” account status and a “current” password. For questions about drug orders, transfers, returns, or accountability, call or email PMB at any time. Refer to the PMB's website for specific policies and guidelines related to agent management.

Transfer of Ixazomib/Placebo: Ixazomib/placebo may **not** be transferred from one patient to another patient or from one protocol to another protocol. PMB does not permit the transfer of agents between institutions (unless prior approval from PMB is obtained). Ixazomib/placebo supplied for this study may not be used outside the scope of this protocol. To obtain an approval for transfer, investigators should complete and submit to the PMB ([contact]) a Transfer Investigational Agent Form available on the NCI home page (<http://ctep.cancer.gov>) or call the PMB at [contact]. The participating institution should also inform the ECOG-ACRIN of the transfer by transferring the patient in TUMS.

Return of Ixazomib/Placebo: At the completion of accrual and treatment, all unused (unopened) blister packs of ixazomib/placebo must be returned to the PMB. When it is necessary to return study drug (e.g., unused blister packs remaining when the protocol is closed to accrual and treatment at a participating clinical site, unopened expired blister packs, or supplies remaining after a patient goes off of protocol treatment), investigators should return the ixazomib/placebo to the PMB using the NCI Return Agent Form available on the NCI home page (<http://ctep.cancer.gov>).

Supplies remaining from dispensed blister cards should be documented on the patient-specific NCI Investigational Agent Accountability Record Form for Oral Agents. On the correct dispensing row, document the date returned and the quantity, then destroy on site in accordance with institutional policy.

Agent Inventory Records: The investigator, or a responsible party designated by the investigator, must maintain a careful record of the receipt, dispensing and final disposition of all agents received from the PMB using the appropriate NCI Investigational Agent (Drug) Accountability Record (DARF) available on the CTEP forms page. Store and maintain separate NCI Investigational Agent Accountability Records for each patient, agent, strength, formulation and ordering investigator on this protocol. **Please note that the Julian Date – Order number (e.g., 21352-0003) from the patient-specific label must be used as the Lot number on the NCI Oral DARF.**

Questions about drug orders, transfers, returns, or accountability should be addressed to the PMB by calling [contact] Monday through Friday between 8:30am and 4:30pm Eastern Time. You may also contact the PMB via e-mail at [contact].

8.1.10 Side Effects

See Section [5.4.1](#) for the Comprehensive Adverse Event and Potential Risks (CAEPR) list.

8.1.11 Potential Drug Interactions

Ixazomib/placebo is metabolized by CYP3A4 (42.3%), 1A2 (26.1%), 2B6 (16%), 2C8 (6%), 2D6 (4.8%), 2C19 (4.8%), and 2C9 (<1%). Co-administration of ixazomib/placebo with clarithromycin did not result in a clinically significant change in the systemic exposure of ixazomib/placebo. Co-administration of ixazomib/placebo with rifampin decreased ixazomib/placebo Cmax by 54% and AUC by 74%. Therefore, avoid concomitant administration of ixazomib/placebo with strong CYP3A4 inducers (such as rifampin, phenytoin, carbamazepine, and St. John's Wort).

Ixazomib/placebo is neither a time-dependent nor a reversible inhibitor of CYP1A2, 2B6, 2C8, 2C9, 2C19, 2D6, or 3A4/5. Ixazomib/placebo did not induce CYP1A2, CYP2B6, and CYP3A4/5 activity or corresponding immunoreactive protein levels. Ixazomib/placebo is not expected to produce drug-drug interactions via CYP inhibition or induction.

Ixazomib/placebo is a low affinity substrate of P-gp. Ixazomib/placebo is not a substrate of BCRP, MRP2 or hepatic OATPs. Ixazomib/placebo is not an inhibitor of P-gp, BCRP, MRP2, OATP1B1, OATP1B3, OCT2, OAT1, OAT3, MATE1, or MATE2-K. Hence, ixazomib/placebo is not expected to cause transporter-mediated drug-drug interactions.

8.2 Lenalidomide

Please refer to the commercial package insert for complete drug and toxicity information.

8.2.1 Other Names

CC-5013, Revlimid™, CDC-501

8.2.2 Classification

Immunomodulatory Agent

8.2.3 Mode of Action

Lenalidomide, a thalidomide analog, is an immunomodulatory agent with a spectrum of activity that is still under investigation. Some of its effects include inhibition of inflammation, inhibition of angiogenesis, inhibition of hematopoietic tumor cell proliferation, modulation of stem cell differentiation and upregulation of T cell and NK cell responses.

8.2.4 Storage and Stability

Storage: Store capsules at room temperature (25°C). Excursions are permitted (to 15-30°C).

Stability: Refer to the package labeling for expiration date.

8.2.5 Dose Specifics

Lenalidomide will be administered at a dose of 10 mg on days 1-28.

8.2.6 Preparation

No preparation is required.

Only a one cycle (28-day) supply may be dispensed at one time.

8.2.7 Route of Administration

Take lenalidomide by mouth with or without food. Do not crush, chew or open capsules.

8.2.8 Availability

Lenalidomide will be provided in accordance with Celgene Corporation's Revlimid REMS® program. Per standard Revlimid

REMS® program requirements, all physicians who prescribe lenalidomide for research patients enrolled into this trial, and all research patients enrolled into this trial, must be registered in, and must comply with, all requirements of the Revlimid REMS® program.

Further information about the Revlimid REMS® program is available at www.celgeneriskmanagement.com.

Celgene distributes lenalidomide 2.5 mg and 5 mg hard gelatin capsules in tamper-evident, child-resistant, opaque, high density polyethylene (HDPE) bottles with HDPE caps.

The capsules also contain anhydrous lactose, microcrystalline cellulose, croscarmellose sodium, and magnesium stearate.

8.2.9 Side Effects

See Section [5.4.2](#) for the Comprehensive Adverse Event and Potential Risks (CAEPR) list.

8.2.10 Potential Drug Interactions

Periodic monitoring of digoxin levels is recommended during coadministration with lenalidomide.

Monitor patients receiving concomitant warfarin per standard practice guidelines.

Lenalidomide is not a substrate of human CYP enzymes, nor is it an inhibitor or inducer.

8.2.11 Nursing/Patient Implications

Risks Associated with Pregnancy

Lenalidomide is structurally related to thalidomide. Thalidomide is a known human teratogenic active substance that causes severe life-threatening birth defects. An embryofetal development study in animals indicates that lenalidomide produced malformations in the offspring of female monkeys who received the drug during pregnancy. The teratogenic effect of lenalidomide in humans cannot be ruled out. Therefore, a risk minimization plan to prevent pregnancy must be observed.

Definition of patient of childbearing potential

A patient of childbearing potential is anyone, regardless of sexual orientation or whether they have undergone tubal ligation, who meets the following criteria: 1) has achieved menarche at some point, 2) has not undergone a hysterectomy or bilateral oophorectomy, or 3) has not been naturally postmenopausal (amenorrhea following cancer therapy does not rule out childbearing potential) for at least 24 consecutive months (i.e., has had menses at any time in the preceding 24 consecutive months).

Before starting study drug:

Patients of Childbearing Potential:

- Patients of childbearing potential must have two negative pregnancy tests (minimum sensitivity of 25 mIU/mL) prior to

starting study drug. The first pregnancy test must be performed within 10 to 14 days prior to the start of study drug and the second pregnancy test must be performed within 24 hours prior to the start of study drug. The patient may not receive study drug until the Investigator has verified that the results of these pregnancy tests are negative.

Male Patients:

- Must agree to use a latex condom during sexual contact with partners of childbearing potential while participating in the study and for at least 28 days following discontinuation from the study even if they have undergone a successful vasectomy.

All Patients:

- Only enough lenalidomide for one cycle of therapy may be dispensed with each cycle of therapy.
- If pregnancy or a positive pregnancy test does occur in a study patient or the partner of a male patient during study participation, lenalidomide must be immediately discontinued.

9. Statistical Considerations

Rev. Add3

9.1 Study Design

This is a randomized phase III study with the primary aim to evaluate whether intensifying maintenance therapy based on MRD positive status after approximately 1 year post early stem cell transplant lenalidomide maintenance results in prolonged overall survival (OS). OS will be compared between patients with MRD positive status (n=510) randomized to either ixazomib-lenalidomide (Arm A) or placebo-lenalidomide (Arm B).

9.2 Study Endpoints

9.2.1 Clinical Outcomes

9.2.1.1 Primary Endpoint

- Overall survival defined as the time from randomization to death due to any cause, or censored at date last known alive

9.2.1.2 Secondary Endpoints

- Progression-free survival defined as the time from randomization until the earlier of progression or death due to any cause, or censored at date of last disease evaluation (Note: Only deaths that occur within 3 months of the last disease evaluation are considered events.)
- Best response on treatment for eligible patients based on standard IMWG criteria as described in Section 6; Response rates for eligible patients including very good partial response (VGPR), complete response (CR) and stringent CR (sCR) at 12-, 24-, 36- and 60-cycles post-randomization
- Incidence of adverse events by worst grade and type for treated patients determined using CTCAE; Rates of worst grade 3 or higher non-hematologic toxicity and overall worst grade 3 or higher toxicity on treatment

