3.2 Step 1 Randomization

Rev. Add3

- _____ 3.2.1 Patient must meet all eligibility criteria in Section [3.1](#) at the time of Step 1 randomization.
- _____ 3.2.2 Patient must not be off lenalidomide maintenance therapy for more than 30 days prior to start of treatment on Step 1 of this protocol.

_____ 3.2.3 Patient must have evidence of residual disease by central MRD testing or by presence of monoclonal protein in serum or urine.

_____ 3.2.4 Patient must have SPEP, UPEP, and serum FLC performed \leq 28 days prior to randomization.
Serum M-protein by SPEP _____ (g/dL)
Date of Test: _____
Urine M-protein light chain excretion by UPEP _____ (mg/24hr)
Date of Test: _____
NOTE: UPEP (on a 24-hour collection) is required, no substitute method is acceptable. Urine must be followed monthly if the baseline urine M-spike is \geq 200 mg/24 hr. Please note that if both serum and urine M-components are present, both must be followed in order to evaluate response.

Serum Free Light Chain
Kappa FLC _____ (mg/dL) or _____ (mg/L);
Lambda FLC _____ (mg/dL) or _____ (mg/L);
Kappa/lambda ratio _____
Date of Test: _____

_____ 3.2.5 Patient must have the following laboratory levels obtained \leq 14 days prior to randomization:

_____ 3.2.5.1 Hemoglobin \geq 8 g/dL
Hemoglobin: _____ Date: _____

_____ 3.2.5.2 Untransfused platelet count \geq 75,000 cells/mm³
Platelet: _____ Date: _____

_____ 3.2.5.3 Absolute neutrophil count (ANC) \geq 1000 cells/mm³
ANC: _____ Date: _____

_____ 3.2.5.4 Calculated creatinine clearance \geq 30 mL/min
Creatinine clearance: _____ Date: _____

_____ 3.2.5.5 Total bilirubin \leq 1.5 times the upper limit of normal (ULN)
Total bilirubin: _____ ULN: _____ Date: _____

_____ 3.2.5.6 SGPT (ALT) and SGOT (AST) \leq 3 times the upper limit of normal (ULN)
SGPT (ALT): _____ ULN: _____ Date: _____
SGOT (AST): _____ ULN: _____ Date: _____

_____ 3.2.6 Patient must not have Grade 2 or higher peripheral neuropathy or grade 1 peripheral neuropathy with pain per CTCAE.

_____ 3.2.7 Patient must not have uncontrolled intercurrent illness.

_____ 3.2.8 Patient must not have Grade 2 or higher diarrhea per CTCAE in the absence of antidiarrheals.

_____ 3.2.9 Patient must not have been on systemic treatment, within 14 days before the first dose of ixazomib, with strong CYP3A inducers (such as rifampin, rifapentine, rifabutin, carbamazepine, phenytoin, phenobarbital), or use of St. John's wort.

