5.8 Duration of Follow-up

For this protocol, all patients, including those who discontinue protocol therapy early, will be followed for response until progression, even if non-protocol therapy is initiated, and for survival for 10 years from the date of randomization. All patients must also be followed through completion of all protocol therapy.

6. Measurement of Effect

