6.2.2.4 Progression (PD)

Patients will be considered to have met progression if one of the following criteria is met. The investigation that qualified as progression should be repeated and verified on a subsequent occasion only if treating physician deems it clinically necessary.

Increase of \geq 25% from lowest value reported in

- Serum M-component and/or (the absolute increase must be \geq 0.5 g/dL).
- Urine M-component and/or (the absolute increase must be \geq 200 mg/ 24 hours).
- Only in patients without measurable serum and urine M protein levels: the difference between involved and uninvolved FLC levels. The absolute increase must be $>$ 10 mg/dL.
- If the only measurable disease is bone marrow, bone marrow plasma cell percentage: the absolute % must be \geq 10%.
- Development of new bone lesions or soft tissue plasmacytomas or \geq 50% increase from nadir in the size (SPD) of existing bone lesions or soft tissue plasmacytoma or \geq 50% increase in the longest diameter of a previous lesion $>$ 1cm in short axis. Plasmacytoma measurements should be taken from the CT portion of the PET/CT, or MRI scans, or dedicated CT scans where applicable. For patients with only skin involvement, skin lesions should be measured with a ruler. Measurement of tumor size will be determined by the sum of the products of the maximal perpendicular diameters of measured lesions (SPD).

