Rev. Add3 7. Serum and urine immunofixation and serum FLC only need to be repeated to confirm sCR or CR.

Rev. Add3 8. Within 8 weeks of pre-registration Step 0.

Rev. Add3 9. Follow-up post-treatment till progression. After progression, follow for survival for a maximum of 10 years. Every 3 months if patient is < 2 years from randomization, every 6 months if patient is 2-5 years from randomization, every 12 months if patient is 5 years or more from randomization. No specific requirements if patient is more than 10 years from randomization.

10. All specimens must be entered and tracked via the online ECOG-ACRIN Sample Tracking System (STS). See Section [10.3](#)

11. End of cycles 12, 24, 36 and 60 (\pm 6 weeks) only

12. End of cycles 12 and 24 (\pm 6 weeks) only

13. Institutions must upload immunofixation test results via Medidata Rave to determine eligibility status for Step 1 randomization.

14. Please refer to Section [8.2.8](#) and www.celgeneriskmanagement.com for information about the Revlimid REMS® program.

15. As clinically indicated.

Rev. Add3 16. Height is only required at baseline (prior to randomization) and does not need to be repeated.

8. Drug Formulation and Procurement

Investigator Brochure Availability

The current versions of the IBs for the agents will be accessible to site investigators and research staff through the PMB OAOP application. Access to OAOP requires the establishment of a CTEP IAM account and the maintenance of an “active” account status, a “current” password and active person registration status. Questions about IB access may be directed to the PMB IB Coordinator via email.

Useful Links and Contacts

- CTEP Forms, Templates, Documents: <http://ctep.cancer.gov/forms/>
- NCI CTEP Investigator Registration: [contact]
- PMB policies and guidelines:
http://ctep.cancer.gov/branches/pmb/agent_management.htm
- PMB Online Agent Order Processing (OAOP) application:
<https://ctepcore.nci.nih.gov/OAOP>
- CTEP Identity and Access Management (IAM) account:
<https://ctepcore.nci.nih.gov/iam/>
- CTEP IAM account help: [contact]
- IB Coordinator: [contact]
- PMB email: [contact]
- PMB phone and hours of service: [contact] Monday through Friday between 8:30 am and 4:30 pm (ET)

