9.3.2 Secondary Clinical Analyses

Progression-Free Survival (PFS)

An important secondary aim is to evaluate whether a response-adapted strategy translates into superior progression-free survival for patients switching to more-intensive treatment. PFS will be estimated using the KM method and compared using the stratified log-rank test. Median PFS on the control arm is assumed to be 18 months based on results from recent clinical trials. Assuming exponential distribution of failures, this study is design to detect a 44% increase in median PFS to 26 months on the experimental arm. This corresponds to a treatment HR approximating 0.70 [monthly hazard rate 0.0385 versus 0.0267]. At 1-sided 2.5% type I error, there is approximately 90% power using a log-rank test to detect this HR given 510 patients uniformly accrued over 3.5y with full information of 319 PFS events at 4.5y (accrual end plus one year). The actual timing of this PFS analysis will depend on accrual. The analysis will not be done before one year after the last patient is randomized. No interim analyses for the PFS comparison will be conducted. The study team will also not consider or declare the experimental arm to be a success based on the PFS endpoint alone.

Response

Response will be tabulated by category. Response rates (sCR, CR, VGPR) will be compared using the chi-squared test for proportions. It is hypothesized that the ixazomib-lenalidomide arm will have higher response rates. Ineligible patients are excluded from the analysis and unevaluable patients are counted in the denominator. Sensitivity analyses will exclude unevaluable patients from the rate calculations. Given 255 patients per arm, there is over 90% to detect a difference of 15% in VGPR rates at 1-sided 2.5% significance assuming a 52.5% overall VGPR rate.

Toxicity

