12.1.3.1 Primary imaging aim

[1] To evaluate the association between baseline ¹⁸F-FDG PET/CT and patient outcomes.

The primary imaging aim consists of evaluating the association between baseline ¹⁸F-FDG PET/CT and patient outcomes, and seeks to address the question of whether abnormal ¹⁸F-FDG PET/CT findings at baseline (i.e., after approximately 1 year of lenalidomide maintenance following an early stem cell transplant) are prognostic of poorer progression-free survival (PFS) and overall survival (OS). The potential association will be analyzed using both quantitative and qualitative ¹⁸F-FDG PET/CT parameters.

Rev. Add3

Quantitatively, the association between baseline SUV-based quantitative ¹⁸F-FDG PET/CT parameters (SUVmax, SUVpeak, MTV, TLG) and PFS will be analyzed through Cox regression. PFS will be defined as the time from randomization until the earlier of progression or death due to any cause. SUV-based quantitative ¹⁸F-FDG PET/CT (qPET) parameters will be analyzed as continuous covariates, and adjustment will be made for potential confounders, including patient age and the randomization stratification factors. In addition, we will formally test whether this association differs by study arm through a statistical interaction term between the qPET parameter and study arm. If this interaction is not significant at the 0.05 level, then a single overall hazard ratio will be estimated for the entire study cohort. We assume that up to 10% of patients may not receive the ¹⁸F-FDG PET/CT at baseline or may have an uninterpretable scan.

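### The 3-month limit on counting PFS deaths is half the 6-month off-treatment visit interval, and FLC-defined progression has no routine repeat FLC behind it

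*Combined protocol and SAP*

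**What the plan says.** **Deaths in PFS.** Section 9.2.1.2 defines PFS as progression or death from any cause, censored at the last disease evaluation, and then adds: "Only deaths that occur within 3 months of the last disease evaluation are considered events". Section 5.8 keeps patients who stop therapy early under observation; they "will be followed for response until progression, even if non-protocol therapy is initiated". Section 7.1, footnote 9, sets the post-treatment visits: 3-monthly before 2 years from randomization, then "every 6 months if patient is 2-5 years from randomization", then yearly. On treatment, evaluation follows the 28-day cycle (5.1.1 and the 7.1 table). The imaging section, 12.1.3.1, gives PFS without the limit: "PFS will be defined as the time from randomization until the earlier of progression or death due to any cause".

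**FLC progression.** Section 6.2.2.4 lists an FLC criterion: "Only in patients without measurable serum and urine M protein levels: the difference between involved and uninvolved FLC levels". Eligibility item 3.2.3 reads: "Patient must have evidence of residual disease by central MRD testing or by presence of monoclonal protein in serum or urine", so a patient can enter on marrow MRD alone. Section 7.1, footnote 7, reads: "Serum and urine immunofixation and serum FLC only need to be repeated to confirm sCR or CR". Footnote 15 leaves FLC after treatment to clinical judgment. Footnote 3, which requires an assay when it is used to judge response, is attached to SPEP and UPEP and not to FLC.

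**PFS analysis.** Section 9.3.2 plans one PFS analysis, with "510 patients uniformly accrued over 3.5y with full information of 319 PFS events at 4.5y" and about 90% power.

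**The concern.** A limit on late deaths makes sense when evaluations have been missed, because progression may have gone unseen. Here the limit is shorter than the scheduled interval, so it also removes deaths in patients who missed nothing. Whether a death counts then depends on whether the patient was still on treatment, which is a post-randomization state. If time off treatment differs by arm, the censoring differs by arm too. The documents do not show that it does, or in which direction.

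The FLC point is also a mismatch between a definition and the schedule that should support it. A patient whose serologic relapse shows only in FLC has a progression criterion but no routine test to detect it. The recorded date may wait for SPEP, UPEP, marrow or imaging to turn positive.

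Section 9.3.2 describes PFS as an important secondary aim and gives it a single analysis, so the definition should be settled before the data are examined.

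**Working it through.** **Inputs.** From 9.3.2: PFS medians of 18 and 26 months, 1-sided 2.5%, 510 patients, uniform accrual over 42 months, analysis at month 54, 319 events. From 9.5: 1:1 allocation, so 255 per arm. From 7.1, footnote 9: visit intervals of 3, 6 and 12 months. Not in the documents, so assumed: the share d of late PFS events that are deaths without progression (5-20%), and the share o of those patients who are off treatment (20-100%).

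**1. Reproduce the plan's event count.** With hazard λ = ln 2 / median, the expected events per arm are 255 × [1 − (e^(−12λ) − e^(−54λ)) / (42λ)].
- Control, λ = 0.0385: 175.4.
- Experimental, λ = 0.0267: 143.6.
- Total 319.0, which matches 319.

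**2. Reproduce the power.** Schoenfeld: Φ(√D/2 × |ln HR| − 1.96). With D = 319 and HR = 18/26 = 0.692, power is 90.7%. With the rounded HR of 0.70 it is 89.0%. Both agree with about 90%.

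**3. Share of deaths that count.** If deaths are spread evenly over a k-month interval, the share within 3 months of the last visit is min(1, 3/k).
- On treatment (about 1 month) or 3-monthly visits kept on time: 1.00.
- 6-monthly visits: 0.50.
- 12-monthly visits: 0.25, but no patient has more than 54 months of follow-up at the planned analysis, so this does not arise there.

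The 3-monthly schedule leaves no slack, and footnote 9 gives no visit window, so a late visit before year 2 could also lose a death.

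**4. Events exposed to the 6-month interval.** Events after month 24, per arm: 255 × (1/42) × [30e^(−24λ) − (e^(−24λ) − e^(−54λ))/λ]. This gives 29.4 control and 29.9 experimental, or 59.4 in total before rounding (18.6% of 319).

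**5. Events censored by the rule:** 59.4 × d × o × 0.5.

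| d | o | Censored | Share of 319 |
|---|---|---|---|
| 5% | 20% | 0.3 | 0.1% |
| 10% | 50% | 1.5 | 0.5% |
| 20% | 100% | 5.9 | 1.9% |

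At the worst case, D = 313.1 and power is 90.2% (HR 0.692).

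**6. FLC.** No arithmetic is possible. After baseline, the only other FLC mark in the 7.1 table, as far as its broken layout can be read, is at discontinuation or progression. That test is triggered by the event and cannot detect it. The footnote wording is intact and does not depend on the table layout. Other scheduled checks are SPEP and UPEP each cycle, marrow at the end of cycles 12, 24, 36 and 60, and PET/CT at the end of cycles 12 and 24.

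**The case against.** The case for leaving the plan alone is mainly about weight.

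- **The loss is small.** The 5.9-event figure needs both assumptions at their extremes. The nearest figure in the documents is the phase II study of this combination (1.3): 64 enrolled, 16 off study for progression, and 14 off for other reasons, so 14/48 = 29%. At about 30% off treatment the loss is 0.4 to 1.8 events. This stands.
- **Bias is small even when forced.** Take d = 20%, with 100% off treatment in one arm and 20% in the other. If the experimental arm has the 100%, HR ≈ 0.692 × (1 − 2.99/143.6) / (1 − 0.59/175.4) = 0.680. Reversed, it is 0.701. With 40% experimental and 20% control it is 0.689. This stands, and 9.3.2 bars claiming success on PFS alone.
- **The rule is prespecified and guards against unseen progression.** That is a fair purpose, but it does not explain a limit set at half the scheduled interval.
- **Half is an upper-end share.** An unscheduled evaluation in a deteriorating patient would restart the window. Agreed.
- **Section 12.1.3.1 may be shorthand.** It may be, but a cross-reference settles the matter.
- **Entry on MRD alone does not imply FLC-only relapse, and the schedule is the same in both arms.** True. The affected subgroup may be small, and any delay is not arm-driven by design. The criterion still lacks a routine test.

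**Conclusion.** The concern holds. The death limit does not fit the trial's own visit schedule: about 50% of progression-free deaths off treatment in years 2-5 would be censored in fully compliant patients, assuming deaths fall evenly between visits and no unscheduled evaluations. The practical effect at the planned analysis is small: 0.3 to 5.9 of 319 events, and power 90.7% to 90.2% at worst, under assumed d and o. A between-arm bias is possible but not established. The plan's event count and power reproduce, so this is not a sample-size error, and OS is unaffected.

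Exposure would grow if accrual were slow, because 9.3.2 ties the PFS analysis to accrual and sets no latest date. With 5-year accrual (an assumption) and analysis one year later, the formula in step 4 gives about 91 events after month 24.

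The FLC mismatch is clear from the text, but its size cannot be derived from the documents. Both parts should be corrected; neither threatens the primary conclusion.

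**What to change.** 1. In 9.2.1.2, count a death without documented progression as a PFS event unless two or more consecutive scheduled evaluations were missed, or count all such deaths. Keep the 3-month version as a sensitivity analysis.
2. In 12.1.3.1, refer to that definition so that the document has one PFS.
3. Reconcile footnotes 7 and 15 of 7.1 with 6.2.2.4, so that FLC is measured alongside SPEP in patients whose serologic progression can be shown only by FLC.

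The cost is one sentence, one cross-reference and two footnote edits. Deaths are already collected through the 10-year survival follow-up, so items 1 and 2 need no new data. Item 3 adds FLC assays, on blood already drawn for SPEP, in a subgroup of unknown size. The statistical price of item 1 is that some deaths will be counted later than a progression nobody observed; on 6-monthly visits a counted death could come up to about 12 months after the last evaluation. The 3-month sensitivity analysis shows whether that matters. The change should be made before PFS is analysed, so that it cannot look data-driven.
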